2.C.4.b. Visit 2 (Baseline Visit): 3-21 days after the screening visit, eligible subjects will return for their baseline visit. Subjects will be instructed in the use of study medication and will take one capsule study medication (0.5 mg dutasteride or pbo) at the baseline visit and again on study day 2, followed by 2 capsules daily for the remainder of the phase 1 12-week treatment period (in order to match capsule number for 2 day naltrexone titration in phase 2). Finally, subjects will be trained to use a paper calendar provided by staff to record their daily drinking and use of the IVR system to record their mood, desire to drink, self-efficacy and daily drinking during weeks 1-4 and 9-12 of phase 1 and 21-24 of phase 2. We considered asking subjects to use the IVR report daily for the 168 days of treatment but considered that this would be an excessive subject burden.

Study visits beyond visit 2, may be conducted remotely by telephone if a participant is unable to come to the clinic due to illness, travel, or other valid concerns (e.g. about exposure to COVID-19) related to traveling to UConn Health. Participants will be sent a one-time use REDCap secure link via email to complete study visit surveys. In the event a

participant is unable to attend an in person scheduled visit, backup supply of medication previously provided may be used or additional medication (up to 8 weeks) will be provided at an earlier visit if inability to attend future scheduled visit is anticipated in advance. Study staff will consult with study physician regarding whether study medication should be continued if a participant reports illness as reason for a missed in person visit. All unused medications will be brought to the next in person study visit.

2.C.4.c. Bi-weekly Clinic or remote Visits 3-14: A brief Timeline Follow-Back (TLFB) interview will be performed to track participants' daily alcohol consumption and medication use since the last study visit, and a trained staff member will deliver the medical management intervention.

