At the end of phase 1 treatment week 12 (visit 8) and phase 2 treatment week 24 (visit 14), subjects will complete a series of questionnaires and be interviewed by research staff concerning their alcohol consumption and alcohol-related symptomatology. For subjects who withdraw early and do not wish to continue with study visits/procedures, end-of-treatment evaluations will be administered at the time of withdrawal. Such subjects will also be invited to participate in-person or by telephone to provide drinking data for the 12-, 24-week time points in order to include this data in intent to treat analysis of the treatment phase.

2.C.4.d. Visits 15 and 16 (3- and 6-month Post-treatment Assessment): To evaluate the durability of treatment effects, patients will be invited to return to the clinic for a post-treatment assessment 3 and 6 months after completion of treatment (if unable to come in person a telephone interview will be conducted). Subjects will be contacted 6-8 weeks after end of treatment and following the 3-month follow-up visit to remind them of their follow-up appointment dates, reinforce maintaining their written drinking diary and to remind female subjects of the importance of continued use of effective contraception for 6 months following treatment. At each follow-up visit, subjects will complete self-report questionnaires and will be interviewed by the research staff. Blood samples for measurement of serum PEth, and 3α -diolG will be obtained. Subjects will be paid \$50 for participating in each post treatment visit.

2.C.5. Medical Management: A study physician will meet with each subject at the beginning of treatment. The PI will consult at least weekly with study staff to monitor potential study-related side effects and will be available to personally evaluate subjects with severe or persistent adverse effects. At each treatment encounter, subjects will receive brief counseling as part of medical management, described below.

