a side effect concern. In other clinical studies, daily doses of 5 mg (i.e., 5 times the daily in the proposed study for alcohol problems) were administered to 60 men for 6 months with no adverse effects beyond those seen at the more commonly used daily dose of 0.5 mg (Avodart, Prescribing information 2012, GlaxoSmithKline). Depression has been reported as a potential side effect of the 5AR inhibitor finasteride in several small retrospective case series (Hirshburg, Kelsey et al. 2016). In the only prospective study examining mood in 128 men treated with finasteride for alopecia, the Beck Depression Inventory (BDI) score increased minimally from 12.11 to 12.80 after 2 months treatment (Rahimi-Ardabili, Pourandarjani et al. 2006). In our current study of dutasteride in men we observed a decrease in BDI scores over the 12-week study period in both dutasteride and placebo arms. A recent large retrospective study of 90,000 men who initiated treatment with a 5α reductase inhibitor (finasteride or dutasteride) during the period 2003-2013 and matched controls found no increased risk of suicide associated with medication but an increased risk of self-harm events (18 per 10,000 exposed vs. 14 per 10,000) and incident depression (194 per 10,000 exposed vs. 137 per 10,000) during the initial 18 months of treatment (Welk, McArthur et al. 2017). In view of these reports of the potential for 5α reductase inhibitors to increase depressive symptoms, we will use the physician's health questionnaire (PHQ-9) to screen for clinical depression at every study visit. The PHQ-9 is a validated 9-item self-report measure of depressive (Ware, Kosinski et al. 1996, Kroenke, Spitzer et al. 2001), a response of 1 or greater on item 9 related to suicidal thoughts will trigger a clinical evaluation by study physician or nurse regarding safety.

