individuals with contraindicated medical and/or psychiatric conditions. Experienced phlebotomists will minimize venipuncture risk. During treatment, patients' substance use and medical and psychiatric status will be closely monitored. Patients with breath or salivary alcohol levels over the legal driving limit or clinical evidence of intoxication will be examined by a study physician and monitored until no longer intoxicated, or referred for appropriate treatment, as clinically appropriate.

Identifying subjects who are inappropriate for study entry because of current alcohol withdrawal: Subjects with prominent signs of physical dependence, and/or medical comorbidities such that study physicians feel they should consider immediate detoxification, will be referred for medical detoxification in a normal treatment setting. The Clinical Institute Withdrawal Assessment (CIWA-Ar) will be used to facilitate assessment of withdrawal, and decisions regarding appropriateness for study entry with respect to physical dependence will be made based on the judgment of study physicians using the CIWA-Ar score of 10 for an approximate cutoff level. All our study physicians have extensive experience in assessing and triaging patients with alcohol withdrawal. Subjects that need detoxification will be referred for detoxification, and may be eligible to begin the study following successful completion of detoxification.

Medication risks: Frequent contact will help identify patients with adverse treatment effects. Patients will be given a card identifying themselves as participants in a study involving dutasteride or naltrexone, and containing the contact numbers of the PI and study nurse. The medication blind will be broken if necessary for emergency assessment or treatment. For example, if the PI determines that an adverse event is serious, unexpected, possibly related to the study drug, and medical intervention is needed, the PI will request from research pharmacy the medication assignment for the subject so that the patient can receive proper treatment. Adverse medication effects will be systematically evaluated and recorded. If serious, patients will be withdrawn from the study and given appropriate treatment and/or referral.

Study staff may request that pharmacy provide medication assignment after completing the 6 month follow-up or if information needed by patient for clinical discussion with their physician, it may requested after completing medication phase of study.

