
Procedures to minimize potential exposure of pregnant women to active study medication (dutasteride or naltrexone) include 1) excluding subjects younger than 35 who may have a greater likelihood of considering pregnancy after starting the study and would need to avoid pregnancy for 6 months following treatment with dutasteride, 2) inclusion requirement of a negative serum bHCG at screening together with monitoring of urine HCG during the 24-week treatment, 3) review of teratogenic risks by study physician with female subjects, 4) agreement by women of reproductive potential to use effective contraception during the study and for 6 months following completion of medication use, 5) monthly contact by study nurse during 6 month follow-up to remind women of importance

of effective contraception. If a patient reports being pregnant or tests positive, she will be immediately withdrawn from study medication treatment, referred for obstetric evaluation, informed as to the study medication she had taken and advised to discontinue drinking alcohol.

Confidentiality: To avoid breach of confidentiality, patients' names will appear only on a consent form, a telephone screening form, the study nurses visit contact information sheet and a "key" form kept by study staff in a locked cabinet. All forms that contain identifying information will be kept double locked (i.e., in a locked cabinet, in a locked room) to maintain their security. All study data forms will contain only the patient's unique study identification number. Prior to final study closure, any links between personal identifiers and each subject's unique study ID will be deleted to generate a de-identified dataset. Patient visits will be scheduled by study staff and no information about the patient will be provided to anyone outside the study team (except in emergencies as defined above) in person or by telephone, except as required by law. The study will be conducted in an outpatient clinic in which treatment is provided to patients who have a variety of problems, not limited to substance abuse. To further help protect participant privacy, a Certificate of Confidentiality from the National Institutes of Health will be in force for this study. This certificate will protect the investigator and immediate study staff from being forced to release any research data that would identify a participant in this study, even under a court order or subpoena.

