Alternative Treatments: The alternative procedures available are counseling by other clinicians, self-help groups such as Alcoholics Anonymous, or more intensive treatment for heavy drinking, including treatment with oral or long-acting injectable naltrexone, disulfiram, or acamprosate, which are FDA-approved medications widely available for treatment of AD. Subjects requesting additional treatment for alcohol problems following completion of the study protocol or withdrawal from the study will be referred to local treatment centers.

3.B.2. Potential benefits to patients and society: Benefits to patients include careful evaluation of their medical and psychiatric status and alcohol use. Benefits to participants also include the potential for reduction in their alcohol consumption with associated improvements in their physical and psychological health, functioning at work and in their family/relationships. Benefits to society include a potential improvement in the effectiveness of treatment for problem drinking, which may reduce the personal and societal burdens associated with heavy drinking. In addition, clinicians and scientists may better understand the effects of dutasteride to reduce alcohol consumption. An improved understanding of phenotypic and genetic predictors and/or moderators of dutasteride response will offer the potential for individualized treatment and enhanced the clinical utility of dutasteride for alcohol use problems.

3.B.3. Importance of Knowledge to be Gained: Alcohol dependence has a major impact on society, families and individuals affected. AUD remains a major health concern, additional treatment options are needed. Results from our recently completed first study of dutasteride for reducing alcohol use indicate is well tolerated and may represent a very effective treatment options especially for subjects who drink to cope with negative emotions. The proposed study seeks to better identify predictors of efficacy to potentially advance medication treatment match for alcohol use treatment.

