AE monitoring. The study nurse will use the SAFTEE instrument to screen for adverse events at each treatment visit. The P.I. will evaluate every moderate or severe adverse event and determine whether it affects the risk/benefit ratio of the study and whether modifications to the protocol or informed consent form are required. The principal

investigator (and, in his absence, physician co-investigators) will differentiate serious from non-serious adverse events.

A Serious Adverse Events Monitoring Form will be used by study staff to provide information about all serious adverse events (expected and unexpected including not study related), how they were handled, and their potential relationship to study participation and a sign-off by appropriate supervisory personnel. Patients who experience a significant psychiatric or medical problem requiring an overnight hospitalization at an acute care facility will be considered to have experienced an SAE. Serious Adverse Events also include adverse events that result in death, a persistent or significant disability/incapacity or result in a congenital anomaly/birth defect.

Serious adverse events (SAEs) and other serious unanticipated events that are possibly related to the study interventions will be reported within 48 hours of study team knowledge of the SAE to the 1) UCHC IRB / Office of the Vice President for Research, 2) the study DSMB, and 3) the NIAAA project officer. All other SAEs, unanticipated events and non-serious adverse events (AEs) during the treatment will be reported to the UCHC IRB, as well as to the NIAAA on an annual basis. SAEs, AEs, and unanticipated problems will be managed consistent with UConn Health IRB guidelines.

Other adverse events will be monitored during study visits or phone calls with participants and reviewed weekly at study staff meeting. An ongoing database of adverse events will be maintained by the study staff. Aggregate data on reports of adverse events will be provided to the DSMB members on a semi-annual basis as part of their semi-annual review with the study staff and PI of data and patient safety monitoring. The following information will be considered in the periodic safety report:

- Number of patients who have completed the study.
- Dropout rates and reasons for the dropouts.
- Summary of adverse events.
- Any other relevant information

The annual report to the NIAAA program officer will include

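### A serious adverse medication effect means withdrawal from the study, not only from medication, so it is unclear whether a willing patient keeps the scheduled side-effect, mood and drinking assessments

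*Combined protocol and SAP*

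**What the plan says.** Protocol Section 3.B.1, Medication risks, states the rule for adverse medication effects: "If serious, patients will be withdrawn from the study and given appropriate treatment and/or referral". It names no later study assessment. The pregnancy paragraph of the same section is narrower: "she will be immediately withdrawn from study medication treatment".

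Section 2.C.4.c deals with early exit. It addresses "subjects who withdraw early and do not wish to continue with study visits/procedures". They receive the end-of-treatment evaluation when they leave, and are invited to report drinking for weeks 12 and 24, in person or by telephone, for the intent-to-treat analysis.

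The Schedule of Assessments places TLFB and PHQ-9 at every visit and SAFTEE at every visit from baseline, including the 3- and 6-month visits. Section 3.A.3 explains that the PHQ-9 is used "to screen for clinical depression at every study visit" because of reports of depression with this drug class. Section 3.C counts as serious "a significant psychiatric or medical problem requiring an overnight hospitalization at an acute care facility", as well as death, lasting disability and birth defect. Section 2.C.4.b adds: "Study visits beyond visit 2, may be conducted remotely by telephone".

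**The concern.** Stopping a drug and leaving a study are different events. A patient taken off medication for a serious reaction can still be seen, and those later observations show whether the reaction resolved. The Medication risks rule merges the two, although the pregnancy paragraph shows that the protocol has narrower wording available.

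Safety follow-up is the main thing at stake. Section 3.A.3 cites a large retrospective study of 5-alpha reductase inhibitors, with incident depression of 194 versus 137 per 10,000 and self-harm of 18 versus 14 per 10,000. A patient hospitalized overnight for depression judged drug-related would meet the Section 3.C definition and, read literally, would leave the serial PHQ-9. Drug effect may also outlast dosing: Section 2.C.3.a describes very slow release from the enzyme, and Section 3.A.3 sets precautions for six months after treatment.

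Completeness of drinking data comes second. Section 2.C.4.c plainly wants week-12 and week-24 drinking from people who leave early. A rule that removes willing patients works against that aim.

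**Working it through.** No figure in the plan depends on this rule, so there is nothing to reproduce. The check has two parts: a comparison of the texts, and a rough count of patients.

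**Texts side by side**

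| Place | What triggers it | What stops | What continues |
|---|---|---|---|
| 3.B.1, Medication risks | Serious adverse medication effect | Study participation | Treatment and/or referral; no study assessment named |
| 3.B.1, pregnancy | Pregnancy | Study medication | Obstetric referral; no study assessment named |
| 2.C.4.c | Early withdrawal by someone not wishing to continue | Visits | Exit evaluation; invitation to report drinking at weeks 12 and 24 |
| 3.C | Any adverse event | Nothing | Review of event outcomes; serious-event form; referral of those at risk |

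1. The first row, taken alone, ends the bi-weekly SAFTEE, PHQ-9 and TLFB.
2. The third row may soften this, but its condition is the subject's own wish. A willing patient removed by the investigator is not clearly covered.
3. If the third row does apply, it gives one SAFTEE and one PHQ-9 at exit, because both belong to the end-of-treatment visit in the Schedule of Assessments. It also gives two invited drinking reports. It adds no bi-weekly SAFTEE or PHQ-9 afterwards.
4. Section 2.C.4.d invites patients to a "post-treatment assessment 3 and 6 months after completion of treatment". Nothing there bars someone who stopped early.

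**How many patients**

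Inputs: no study-related serious adverse effects in the prior trial; 142 randomized (74 to dutasteride) and 135 in its modified intention-to-treat sample (Section 2.B.2). This trial plans 190 randomized, 95 per arm, with 160 completing phase 1 (Section 2.C.2 and Table 1).

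With no events in n patients, the exact one-sided 95% upper bound is 1 − 0.05^(1/n).

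- Both arms, n = 142: 1 − 0.05^(1/142) = 2.09%; × 190 = 4.0 patients.
- Both arms, n = 135: 2.19%; × 190 = 4.2 patients.
- Dutasteride arm, n = 74: 3.97%; × 95 = 3.8 patients.
- Dutasteride arm, n = 67: 4.37%; × 95 = 4.2 patients. This denominator is used because the reported 16.4% and 9.0% equal 11/67 and 6/67, whereas 12/74 = 16.2% and 7/74 = 9.5%.

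The range is therefore 0 to about 4 patients. By comparison, the plan already expects 190 − 160 = 30 non-completers, or 15 per arm if split evenly.

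**Ceiling on unobserved drinking weeks in phase 1, dutasteride arm**

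The arm has 95 × 12 = 1,140 patient-weeks. At the upper bound, assuming withdrawal at week 6 or at week 1 and no later retrieval:

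- Week 6: 3.77 × 6 = 22.6 to 4.15 × 6 = 24.9 weeks (2.0% to 2.2%).
- Week 1: 3.77 × 11 = 41.5 to 4.15 × 11 = 45.7 weeks (3.6% to 4.0%).

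This overstates the likely loss. TLFB asks about each day since the last visit, so a single week-12 contact could recover some or all of these weeks.

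**The case against.** The strongest reply is that Section 3.B.1 is loosely worded and Section 2.C.4.c governs. By singling out withdrawn subjects who do not want more visits, Section 2.C.4.c implies that others withdraw and keep attending. The literal reading of Section 3.B.1 would give a willing patient less follow-up than an unwilling one, which is unlikely to be intended. This argument stands as far as intent goes. It does not settle what staff should do, because neither section mentions withdrawal by the investigator.

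Three further replies also carry weight.

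- The pregnancy paragraph names no later assessment either, so the contrast shows inconsistent wording rather than a deliberate end to follow-up.
- The Alternative Treatments paragraph says that subjects who ask for more treatment "following completion of the study protocol or withdrawal from the study will be referred to local treatment centers". Pairing completion with withdrawal in this way hints that withdrawal ends participation, but the sentence is about referral and is weak evidence.
- The PHQ-9 is there to screen. A patient already hospitalized for depression has been detected, and Section 3.C keeps outcome review, the serious-event form and referral. What might be lost is serial scoring on the study schedule, not clinical oversight.

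A reader might infer that the rule ends all safety and drinking follow-up for these patients. The documents do not support that, given the provisions in Sections 2.C.4.c, 2.C.4.d and 3.C.

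**Conclusion.** The point holds as an inconsistency with a cheap remedy. The Medication risks rule says study where it most likely should say study medication. Followed literally, it drops a willing patient from the bi-weekly SAFTEE, PHQ-9 and TLFB for a possibly drug-related reason. Drinking data are reduced rather than clearly ended.

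The size is small: 0 to about 4 patients, with an observed rate of zero in the prior trial. The count assumes that serious in Section 3.B.1 means a study-related event of the kind defined in Section 3.C. It also assumes that a 12-week rate seen in men carries over to a trial that includes women and adds a second 12-week phase with naltrexone. Either assumption could fail.

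A reader might also infer a threat to power or to the treatment comparison. None is claimed. The count is small beside 30 planned non-completers, and the modified intention-to-treat analysis in Section 2.C.9.a.2 uses whatever outcome data exist for anyone with a post-randomization visit. Priority is optional to modest, resting on safety follow-up and low cost.

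**What to change.** In Section 3.B.1, Medication risks, replace withdrawal from the study with withdrawal from study medication. Add one sentence: scheduled SAFTEE, PHQ-9 and TLFB continue, by telephone where needed as Section 2.C.4.b already allows, unless the patient withdraws consent. Treatment and referral stay as written.

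The cost is one phrase, one sentence and slight staff time for a handful of patients at most, some of whom will decline or be unreachable. Where the assignment has been disclosed for emergency care, later drinking reports will have been collected after unblinding and should be read that way.

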The proposed study will extend these results by including both sexes and extend our analysis of the relationship of baseline drinking to cope (DTC) and anxiety by adding baseline standardized questionnaires measuring trait anxiety (STAI), early life adversity (ACES), and a perceived stress scale (PSS) which in other settings was more predictive of health care utilization than stressful life event counts (Cohen, Kamarck et al. 1983). Women are expected to have a greater likelihood of elevated DTC, ACES, trait anxiety scores (Smith and Randall 2012) which will enrich our sample in subjects potentially more responsive to dutasteride vs. pbo. We will use separate randomizations for women vs. men and include dichotomized scores for DTC and *FKBP5* risk allele carrier status in our URN randomization to balance for these potential predictors of efficacy. This study may identify easy to score pre-treatment measures such as the CDMQ, ACES, STAI, PSS and genotype that could be clinically useful for making personalized treatment recommendations regarding use of dutasteride to reduce heavy drinking.

2.C. Experimental Approach / Research Plan

2.C.1. General Design: The study will be conducted in the UCHC Clinical Research Center (CRC) clinic. Random assignment to initial treatment group and double-blind conditions will be maintained throughout the study. The study consists of two 12-week phases (**Table 1**), the first being a 12-week parallel-groups comparison of dutasteride and pbo to evaluate the safety and efficacy of dutasteride 1 mg/day in reducing the likelihood of drinking and heavy drinking in a sample of treatment-seeking men and women with AUD. In the second 12-week phase, responders in phase 1 (defined as a ≥60% reduction in SD/wk for weeks 9-12 compared with screening) will continue on their initial medication assignment, while non-responder subjects treated with placebo will cross over to dutasteride, and non-responder subjects treated with dutasteride will cross over to naltrexone. This design maintains double blind conditions in both phases 1 and 2 and is innovative. This design will: i) promote retention and recruitment, as subjects who do not respond to treatment in phase 1 will cross-over to an active FDA approved medication for AUD, ii) provide two comparisons to examine dutasteride efficacy, a between-subjects

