- Confirmation of adherence to the data and safety monitoring plan;
- Summary of all AEs;
- Summary of any data and safety monitoring issues that occurred since the previous reporting period;
- Description of any changes in the research protocol or the data and safety monitoring plan that potentially affect risk;
- Summary of all new IRB approvals during the report period.

Any patients thought to be at risk from drinking or psychiatric or medical disorders during treatment or the follow-up period will be referred to services at UCONN Health or to other local health service providers.

Data Monitoring. Data entry will occur at the time of visit via REDCap directly by staff or study subjects (with supervision by staff). Other data not entered at time of visit will be doubly entered via REDCap feature to assure accuracy of entry. All study staff involved in data entry are blind to treatment condition. The PI will have primary responsibility for data accuracy and compliance with protocol.

A Data Safety and Monitoring Board (DSMB) for the study will be established prior to enrollment of patients. This committee will be asked to review semi-annually study data regarding enrollment, safety and adverse events. The committee may make recommendations for early stoppage of the trial based on review of study data. DSMB members will be provided with semi-annual reports to include data that inform progress of the study, including recruitment data, and adverse events data. These data will be used to decide whether to 1) continue recruitment as planned, 2) continue with a protocol amendment, or 3) stop recruitment pending investigation. The DSMB will typically hold meetings electronically or by conference call.

Study suspension / stopping. A decision to discontinue the study will be based primarily on consideration by the DSMB of study related serious adverse events (SAE's). DSMB members will receive a copy of the Serious Adverse Events Monitoring Form within 48 hours of study team knowledge of the SAE, at which point DSMB members will make one of two recommendations: 1) continue recruitment and treatment as planned; 2) schedule a formal meeting within one week to determine if the study should: a) continue study unchanged; b) continue recruitment after a protocol amendment; or c) stop recruiting and if appropriate treatment pending further investigation.

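### Study staff may request individual assignments before the trial ends, in some cases before the 3- and 6-month follow-up interviews, which sits poorly with a blind said to hold throughout the study

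*Combined protocol and SAP*

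**What the plan says.** Section 3.B.1 (Medication risks) first covers emergency unblinding, which is not at issue. A separate sentence then gives two non-emergency routes.

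- Routine: "Study staff may request that pharmacy provide medication assignment after completing the 6 month follow-up".
- Need-based: "or if information needed by patient for clinical discussion with their physician, it may requested after completing medication phase of study". This opens at week 24, before visits 15 and 16.

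The sentence does not mention the last patient, database lock, which staff may ask, who receives the answer, a log, or any bar on later assessment by someone who has learned an assignment.

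Other sections describe the blind as follows.

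- 2.C.1: "Random assignment to initial treatment group and double-blind conditions will be maintained throughout the study", and later in the same paragraph, "This design maintains double blind conditions in both phases 1 and 2 and is innovative".
- 3.C (Data Monitoring): "All study staff involved in data entry are blind to treatment condition". That section also has data entered during visits, by staff or by participants whom staff supervise.

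On the follow-up visits, 2.C.4.d says: "At each follow-up visit, subjects will complete self-report questionnaires and will be interviewed by the research staff". Both 2.C.1 and 2.C.4.d give durability of effect as their purpose. Section 2.C.6.b.4 places the timeline follow-back (TLFB) drinking interview and the SAFTEE side-effect checklist at both visits.

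**The concern.** The release rule works patient by patient, while recruitment and treatment run for years. Two kinds of data could be affected.

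**Directly**, a patient whose assignment is released after week 24 can reach the 3- and 6-month visits knowing it, and the interviewer may know it too. TLFB asks the patient to recall drinking on each day since the last visit, and SAFTEE is a self-report of side effects. Both can shift with knowledge of the arm. The plan's check on the blind, the medication questionnaire in 2.C.6.b.3, is completed at the end of phases 1 and 2, so it would not pick up a later release.

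**Indirectly**, staff who learn the arms of finished patients may still conduct TLFB interviews, counsel, and screen for adverse events in patients on blinded treatment. The two primary outcomes, heavy drinking days and drinks per week, come from those TLFB interviews (2.C.9.a.2). Seeing which assignments went with which course gives staff grounds for guessing the arms of current patients.

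**Working it through.** The plan states no figure on this point, so there is nothing to reproduce. The check has two parts: how long the window is, and which data fall inside it.

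**Inputs.** 190 to be randomised and 160 expected to complete phase 1 (2.C.2); 5 randomised per month (Table 3); 24 weeks of treatment, then follow-up to 6 months (2.C.4.d). Assumptions: even accrual and, at first, no dropout. One month is 365.25/12/7 = 4.348 weeks.

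**Timeline.**

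1. Recruitment: 190/5 = 38 months.
2. Week 24: 24/4.348 = 5.52 months after randomisation. The 6-month follow-up: 5.52 + 6 = 11.52 months.
3. The need-based route first opens at month 5.52, with 5 × 5.52 ≈ 28 randomised and about 162 (85%) still to come.
4. The routine route first opens at month 11.52, with 5 × 11.52 ≈ 58 randomised and about 132 (70%) still to come.
5. At the last randomisation, (38 − 11.52) × 5 = 132.4 patients are past their 6-month visit and (38 − 5.52) × 5 = 162.4 are past week 24. These match steps 3 and 4 because accrual is even.
6. Applying the planned phase 1 completion, 160/190 = 0.842: 132.4 × 0.842 ≈ 111 and 162.4 × 0.842 ≈ 137.
7. Without dropout, at 4 per month the counts in step 5 are 144 and 168; at 6 per month they are 121 and 157. The share still to be randomised when routine release first opens runs from 76% (4 per month) to 64% (6 per month).
8. The last 6-month visit falls at 38 + 11.52 ≈ 49.5 months, 38 months after the first patient's.

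These counts show who could become eligible for release. They do not forecast requests, whose frequency the documents do not give.

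**What is exposed.**

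- *A treatment completer's own phase 1 and 2 drinking outcomes:* not exposed. Both routes open after week 24.
- *The same patient's month-3 and month-6 TLFB and SAFTEE data:* exposed under the need-based route only. Sections 2.C.9.a.1 and 2.C.9.a.2 specify no analysis of them. Blood PEth, also taken at these visits, is a laboratory measure and less vulnerable.
- *Patients still on treatment:* exposed indirectly under either route, if the staff who learn assignments also assess or counsel.
- *Early withdrawers:* unclear. Section 2.C.4.c still seeks their 12- and 24-week drinking data, and 3.B.1 does not say whether they count as having completed the medication phase.

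**The case against.** The strongest reply is that nothing analysed is touched for the released patient. Efficacy comparisons cover phases 1 and 2, safety comparisons cover the same phases, and the follow-up visits have a purpose but no analysis. For treatment completers this stands, and it limits the weight of the point. It does not answer the indirect exposure.

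A second reply is that the blind was only meant to cover treatment. Section 2.C.1 describes two 12-week phases and says that the blind holds in both. That reading is possible, but the same paragraph promises blinding throughout the study. Even on the narrower reading, release to staff during other patients' treatment bears on those patients' blinding. The statement in 3.C is limited to staff involved in data entry, but because data are entered at visits it can include those who see patients.

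Some stronger inferences are tempting, and the documents do not support them.

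- *That any patient may have the assignment at week 24 on request.* The early route requires a need tied to a discussion with the patient's physician.
- *That assignments necessarily pass through staff.* Staff may make the request; the recipient is not stated. The gap is that nothing prevents staff from receiving them.
- *That urn allocation becomes predictable.* Releases lag randomisation by at least about 28 patients, and the documents give no urn parameters. Any effect is unquantified and probably small.
- *That side-effect guessing depends on this rule.* The group already knows from its completed trial in men that reduced libido was reported by 9.0% on dutasteride against 0% on placebo (2.B.2). Release could strengthen such guesses, but they are possible without it.

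**Conclusion.** The point holds as a stated rule that permits avoidable unblinding during the trial and sits poorly with 2.C.1 and 3.C. Its reach is the month-3 and month-6 interview data of patients released early, and, indirectly, the conduct of assessments in patients still on blinded treatment. A reader might infer that the phase 1 comparison is itself unblinded. The documents do not support that for treatment completers, whose phase 1 and 2 data are already recorded when either route opens.

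The size is an upper bound: about 132 patients eligible by the routine route and 162 by the need-based route before enrolment ends, at 5 per month with even accrual and no dropout. With the plan's 160/190 completion the figures are about 111 and 137. How many releases would occur, and how far they would bias the data, cannot be derived from the documents. The change is worth making because it is cheap: the pharmacy already holds the code.

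**What to change.** Amend 3.B.1 and reconcile it with 2.C.1, with the confidentiality text in 3.B.1, and with 3.C.

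1. Defer routine release until after the last patient's last visit or database lock.
2. For need-based requests after the medication phase, have the pharmacy release the assignment to the patient or, with the patient's written authorisation, to their physician. It should not go to or through staff who assess, counsel or enter data. The authorisation is needed because the confidentiality text bars giving patient information outside the study team except in emergencies or where the law requires it.
3. Log each release with its date and recipient.
4. Flag follow-up records collected after a release, since the patient's own reports are then unblinded even if the interviewer's are not. Report any durability summary with and without them.
5. State whether early withdrawers count as having completed the medication phase for this purpose.
6. Leave emergency, pregnancy and DSMB unblinding as written.

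If releases have already taken place, list them and apply step 4 to the affected records.

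The cost is a short amendment across these sections, an authorisation form and a pharmacy log. The real downside is delay: if routine disclosure waits for the last visit, the earliest patients wait up to about 38 months beyond their own 6-month follow-up. The need-based route remains open to them.
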